#### 9.3.1. Relationship of Adverse Events to Study Vaccine

A related AE is an event where the investigator determined that the relationship to study vaccine was "Possibly Related", "Probably Related" or "Definitely Related".

Related AEs will be summarized for pIMDs and Other AESI.

If a subject reports multiple occurrences of the same AE, only the most closely related occurrence will be presented.

# 9.3.2. Intensity of Adverse Event

Summaries of the number and percentage of subjects with at least one unsolicited AE up to 28 days post-vaccination, one related unsolicited AE up to 28 days post-vaccination, and one related immediate unsolicited AE will be provided by intensity (grade 1 to grade 4). Each SOC (in internationally agreed order) and PT (in alphabetical order) separately will also be presented by intensity.

In the AE intensity tables, if a subject reported multiple occurrences of the same AE, only the most severe will be presented.

#### 9.3.3. Serious Adverse Events

An SAE is any untoward medical occurrence (whether considered to be related to the study vaccine or not) that, at any dose:

- Results in death;
- Is life-threatening (at the time of the event);

Note: the term "life-threatening" in the definition of an SAE refers to an event that put the subject at risk of death at the time of the event; it does not refer to an event that hypothetically might have caused death if it were more severe;

- Requires inpatient hospitalization (≥ 24 hours) or prolongation of existing hospitalization (elective hospitalizations/procedures for pre-existing conditions that have not worsened are excluded);
- Results in persistent or significant disability/incapacity;
- Is a congenital abnormality/birth defect;
- Is another medically important event.

In addition to being presented by gender (Both, Male and Female), race (All, Caucasian or White; Black or African American; Asian) and prior vaccine status (Both, Yes and No), if >25% of the enrolled subjects have received a standard influenza vaccine during the 12 months prior to study vaccination, for the overall population (65 years of age and older) as indicated in section 9.1, summaries of the number and percentage of subjects with at least one SAE will be presented by SOC and PT for following time period separately (based on AE analysis start date):

• from Day 1 up to Day 28;

Confidential

Medicago USA Page 38 of 55

- from Day 29 up to Day 182;
- from Day 183 up to the end of study (Day 365).

At each level of subject summarization, a subject is counted once if the subject reported 1 or more events.

All SAEs will be presented in a listing separately. If there are no SAEs at the end of the study, the tables or listings will state that there are no SAEs in the study.

## 9.3.4. Adverse Events of Special Interest

AESI includes following categories, which will be presented in separate tables:

- Related Hypersensitivity Reactions identified using both narrow and broad standardized MedDRA® queries;
- Narcolepsy identified using MedDRA PT Narcolepsy;
- pIMDs and Other AESI (refer to Appendix 13.4).

In addition to being presented by gender (Both, Male and Female), race (All, Caucasian or White; Black or African American; Asian) and prior vaccine status (Both, Yes and No), if >25% of the enrolled subjects have received a standard influenza vaccine during the 12 months prior to study vaccination, for the overall population (65 years of age and older) as indicated in section 9.1, summaries of the number and percentage of subjects with at least one of these AESIs will be presented by SOC and PT for following time period separately (based on AE analysis start date):

- from Day 1 up to Day 28;
- from Day 29 up to Day 182;
- from Day 183 up to the end of study (Day 365).

Also, subjects with at least one related pIMDs and Other AESI and with at least one related Narcolepsy will be summarized in the same way.

At each level of subject summarization, a subject is counted once if the subject reported 1 or more events.

All AESIs will be presented in a listing separately.

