10.2 Safety

10.2.1 Evaluations

Safety and tolerability will be evaluated by solicited local and systemic AEs (immediate AEs within 30 minutes post-vaccination and solicited AEs up to seven days post-vaccination), unsolicited AEs up to 28 days post-vaccination (including immediate unsolicited AEs within 30 minutes post-vaccination), and SAEs, AESIs, MAAEs, NOCDs, and AEs leading to withdrawal up to the end of the study. In addition, events will be monitored for a possible hypersensitivity component and potential immune-mediated diseases from all reported events during the study (collected AEs, SAEs, AESIs, NOCDs, and AEs leading to withdrawal). Clinical safety methods will include repeated urine, blood chemistry and haematology testing.

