13.1.3 Adverse Events of Special Interest

13.1.3.1 Adverse Events of Special Interest for QVLP

13.1.3.1.1 Hypersensitivity Reactions

In the eight studies completed to date, all reported events were monitored for a possible hypersensitivity component (events were searched using both narrow and broad standardized MedDRA® queries). Based on the data available so far, there is no definitive evidence of anaphylaxis associated with use of QVLP in humans. However, one subject who received QVLP experienced a possible, truncated anaphylactic reaction assessed as possibly related to the vaccine by the Investigator. Also, a small number of subjects had potential hypersensitivity reactions judged to be related to vaccine administration (no more than 0.5 % of subjects in any given VLP treatment group experienced one of these events) and these events were distributed fairly evenly among treatment groups, including the placebo and the active comparator groups. However, since severe reactions are considered to be an important potential risk (based on the theoretical risk that using plants for the production of biotherapeutics may induce hypersensitivity) the Sponsor will continue to require that appropriate medical treatment and supervision are available to manage any possible anaphylactic reactions. Further, to collect

Confidential Information

additional data on these events, Medicago will closely monitor and assess anaphylaxis and severe allergic reactions (grade 3 and above) assessed as related to the Investigational product as AESIs.

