### 9.1. Incidence of Adverse Events

An overall summary of the number and percentage of subjects will be presented for following categories:

- Immediate solicited and unsolicited AEs
- Immediate solicited AEs
- Immediate unsolicited AEs
- Solicited AEs:
  - Grade 3 or higher solicited AEs
  - Solicited local AEs
  - Solicited Systemic AEs

Medicago USA Page **34** of **55** 

Statistical Analysis Plan, Version 5.0

Date Issued: 14MAR2022

- Unsolicited AEs:
  - Related unsolicited AEs
  - o Grade 3 or higher unsolicited AEs
  - o Grade 3 or higher related unsolicited AEs
- Any SAE
- Any related SAE
- Any related Hypersensitivity reactions
- Any Potential Immune-Mediated Diseases (pIMDs) and other AESI
- Any related pIMDs and other AESI
- Any MAAE
- Any related MAAE
- Any NOCD
- Any related NOCD
- Any AE leading to discontinuation
- Any related AE leading to discontinuation
- Any AE leading to deaths
- Any related AE leading to deaths
- Any clinically significant lab data

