#### 9.3. Unsolicited Adverse Events

An adverse event (AE) is defined as any untoward medical occurrence in a subject or clinical investigation subject who was administered a pharmaceutical product, with or without a causal relationship with the treatment.

For the purpose of inclusion in AE tables, incomplete data will be imputed based on section 4.3. Subsequently, AEs might be reclassified as medical history based on the rules described in the same section.

All AEs will be classified by System Organ Class (SOC) and Preferred Term (PT) according to the Medical Dictionary for Regulatory Activities (MedDRA, version 23.1 or later).

Summaries of the number and percentage of subjects with AEs will be provided by SOC (in internationally agreed order) and PT (in alphabetical order) separately. At each level of subject summarization, a subject is counted once if the subject reported 1 or more events.

Percentages will be calculated out of the number of subjects in the SAS population.

Subjects with at least 1 AE will be summarized by treatment group as a whole.

For the following categories, AE information will specifically be presented by gender (Both, Male and Female), race (All, Caucasian or White; Black or African American; Asian) and prior vaccine status (Both, Yes and No), if >25% of the enrolled subjects have received a standard influenza vaccine during the 12 months prior to study vaccination, for the overall population (65 years of age and older):

- Unsolicited AEs for 28 days following study vaccine administration;
- Immediate unsolicited AEs up to 30 minutes after vaccination;
- SAEs;
- Related Hypersensitivity Reactions (AESI);
- Narcolepsy
- pIMDs and Other AESI;
- MAAEs;
- NOCD;
- AEs leading to study discontinuation;
- AEs leading to death;
- Most frequent (defined as  $\geq 1.0$  % of subjects in one of AdjQVLP treatment groups) unsolicited AEs within 28 days after vaccination.

Subject AE data including specific details will be presented in listings.

Medicago USA Page 37 of 55

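### For hypersensitivity only, the SAP counts any related query hit of any grade as an AESI, while the protocol counts anaphylaxis and related grade 3+ allergic reactions

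*SAP*

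**What the plan says.** Protocol 13.1.3.1.1 states what will be followed as a hypersensitivity AESI in this trial: "anaphylaxis and severe allergic reactions (grade 3 and above) assessed as related to the Investigational product as AESIs". The same section mentions the narrow and broad query search only when describing past work: "In the eight studies completed to date, all reported events were monitored for a possible hypersensitivity component". Protocol 10.2.1 separately plans a general watch in this trial, in which "events will be monitored for a possible hypersensitivity component and potential immune-mediated diseases from all reported events during the study"; it names no query and does not call the results AESIs.

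SAP 9.3.4 gives the AESI category as "Related Hypersensitivity Reactions identified using both narrow and broad standardized" MedDRA queries. The overview in SAP 9.1 has a row for "Any related Hypersensitivity reactions", and the subgroup list in SAP 9.3 carries "Related Hypersensitivity Reactions (AESI", labelled as an AESI. None of the three sets a grade limit. SAP 9.3.1 adds no severity condition: "A related AE is an event where the investigator determined that the relationship to study vaccine was" possible, probable or definite.

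Protocol 10.2.2.1 and SAP 3.2.1 both list AESI occurrence, in three periods to Day 365, among the primary safety endpoints. SAP section 11 lists departures from the planned analysis, including the choice of Fisher's test alone, but not this one.

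**The concern.** A related grade 1 or 2 event picked up by the queries is an AESI under the SAP and not under the protocol. Protocol 13.1.6 has investigators report AESIs within 24 hours, and they will use the protocol's definition. The SAP table is filled from a query search instead, so the AESIs reported and the AESIs tabulated can differ for the same endpoint.

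There is also a collection problem. Protocol 13.1.2 records all unsolicited events only to Day 28. From Day 29 it keeps SAEs, events leading to withdrawal, AESIs, MAAEs and NOCDs. After Day 28, a grade 1 or 2 query hit reaches the database only if it qualifies through one of those other routes. Under the SAP definition, the count for the first period therefore rests on fuller collection than the two later counts.

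**Working it through.** The point rests on comparing the texts. The documents state no expected AESI count, so there is no plan figure to reproduce.

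**Step 1: how each definition classifies an event**

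| Event | Protocol 13.1.3.1.1 | SAP 9.3.4 |
|---|---|---|
| Related allergic reaction, grade 3 or above, found by the queries | AESI | AESI |
| Related query hit, grade 1 or 2, not anaphylaxis | not an AESI | AESI |
| Anaphylaxis judged unrelated | unclear: the relatedness condition may or may not apply to anaphylaxis | not an AESI |

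The second row is the conflict. The third row is an ambiguity within the protocol.

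**Step 2: can the protocol's count be read from another planned table?** The overview in SAP 9.1 has a row for related unsolicited events of grade 3 or higher, but it covers every kind of event. SAP 9.3.2 tabulates related unsolicited events to Day 28 by grade within SOC and PT, so the relevant PTs would have to be picked out. Adding PT rows could count a subject twice. After Day 28 no table by grade is planned. SAP 9.3.4 gives SOC and PT by period, without grade, plus a listing. The combined count is not produced.

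**Step 3: scale, for illustration**

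Inputs:
- Protocol 1.3.1: potential hypersensitivity reactions judged related in no more than 0.5% of QVLP recipients, with no grade limit stated.
- Protocol 1.3.1: one possible anaphylactic reaction among 14,409 QVLP recipients (14,258 + 151 from Protocol 1.3).
- Protocol Table 4: 40 per group, 120 in total.

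Formula: P(at least one) = 1 − (1 − p)^n.

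*Any related hit, SAP-type definition, p = 0.005.* Expected number: 40 × 0.005 = 0.20 per arm and 120 × 0.005 = 0.60 overall. P = 1 − 0.995^40 = 18.2% and 1 − 0.995^120 = 45.2%.

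*Protocol-type definition.* The documents give no rate for related grade 3+ allergic reactions, so p is an assumption, shown over a range:

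| Assumed p | P in 40 | P in 120 |
|---|---|---|
| 1/14,409 (the possible anaphylaxis only) | 0.28% | 0.83% |
| 0.1% | 3.9% | 11.3% |
| 0.5% (every such event severe) | 18.2% | 45.2% |

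The two counts separate only when a hit is below grade 3. At the 0.5% ceiling, the chance of that in 120 subjects lies between zero (all hits severe) and 45.2% (the chance of any hit at all).

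**The case against.** The strongest reply is that the SAP category only widens the protocol's. Nothing in the documents shows that it loses a related grade 3+ reaction. Protocol 10.2.1 plans hypersensitivity monitoring across all reported events, so a query search is consistent with the protocol. The earlier 0.5% figure also has no grade limit, so the SAP's table is the one comparable with past data. At that rate an arm of 40 has no hit about 82% of the time (100% − 18.2%), and both definitions then give zero. All of this stands, and it supports keeping the query table. It does not support labelling every hit as an AESI, because Protocol 10.2.1 sets that monitoring apart from the AESI definition.

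A reader might infer more than the documents support:

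- *That a severe reaction would be hidden among mild ones.* The AESI categories are tabulated separately by SOC and PT and are also listed. Related unsolicited events to Day 28 are shown by grade. A severe reaction could be found; only its ready-made count is missing.
- *That one mild hit, at 1/40 = 2.5%, would show five times the earlier 0.5%.* Any single event in an arm of 40 is 2.5%, including a true grade 3+ reaction. The ratio reflects the arm size and says nothing about the definition.
- *That the whole AESI endpoint has two definitions.* Narcolepsy is identified by the same preferred term in both documents. SAP 9.3.4 puts the categories in separate tables, so no pooled AESI count is specified for this one to distort.

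**Conclusion.** Wrong as written, but minor. For the hypersensitivity category, following the SAP can give a primary safety endpoint count that differs from the protocol's, and section 11 does not disclose this. The mismatch is conditional: it appears only if a related grade 1 or 2 query hit occurs. It affects descriptive AESI counts and their comparability across the three periods. SAP section 9 plans no safety tests, so error rates and power are untouched, and the 24-hour reporting duty in Protocol 13.1.6 is unchanged.

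The text comparison needs no assumption. The probabilities do. They apply the 0.5% ceiling from earlier QVLP studies, none of which used AS03, to all three current arms, and they leave out the stopped groups, whose sizes are not given. They are a guide to scale only. How many low-grade events the search would return cannot be judged, because the SAP does not name the queries.

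**What to change.** In SAP 9.1, 9.3 and 9.3.4, tabulate the protocol-defined hypersensitivity AESI (anaphylaxis plus related allergic reactions of grade 3 or above) by period as the endpoint. Keep the narrow and broad query hits as a supportive hypersensitivity table under a different label, name the queries, and footnote that grade 1 and 2 events are fully collected only to Day 28. State whether the relatedness condition applies to anaphylaxis. Record the change in section 11.

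The cost is one filter and one additional row or table, using grade and relationship data that are already collected. A grade 3+ row in the existing table with a clear footnote would also supply the missing count, provided the remaining hits are not presented as protocol AESIs.

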13.1.3.2.2 Potential Immune-Mediated Diseases and Other AESI as Listed in Section 19.5

These important potential risks remain "theoretical" as they were for other vaccines containing adjuvants and hence will be collected as AESIs. Potential immune-mediated diseases (pIMDs) are a subset of AEs that include autoimmune diseases and other inflammatory and/or neurologic disorders of interest which may or may not have an autoimmune aetiology. Adverse events that need to be recorded and reported as pIMDs include those listed in Section 19.5.

However, the Investigator will exercise their medical and scientific judgement in deciding whether other diseases have an autoimmune origin (that is pathophysiology involving systemic or organ-specific pathogenic autoantibodies) and should also be recorded as a pIMD.

When there is enough evidence to make any of the diagnoses mentioned in Section 19.5, the AE must be reported as a pIMD. Symptoms, signs or conditions which might (or might not) represent the above diagnoses, should be recorded and reported as AEs but not as pIMDs until the final or definitive diagnosis has been determined, and alternative diagnoses have been eliminated or shown to be less likely.

In order to facilitate the documentation of pIMDs in the eCRF, a pIMD standard questionnaire and a list of preferred terms (PTs) and PT codes corresponding to the above diagnoses will be available to Investigators at study start.

Once a pIMD is diagnosed (serious or non-serious) in a study subject, the Investigator (or designate) must complete, date and sign an Adverse Events Report Form.

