19 APPENDICES

The clinical documents included in the appendices are meant as examples only; the actual documents used during the trial may differ slightly.

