Cranial nerve disorder

Cranial nerve palsies multiple

Cranial nerve paralysis

CREST syndrome Crohn's disease

Cutaneous lupus erythematosus

Cutaneous sarcoidosis Cutaneous vasculitis

Demyelinating polyneuropathy Demyelination

Dermatitis bullous

Dermatitis herpetiformis

Dermatomyositis
Diffuse vasculitis

Encephalitis allergic

Encephalitis autoimmune Encephalitis brain stem

Encephalitis haemorrhagic

Encephalitis periaxialis

diffusa

Encephalitis post immunisation

Encephalitis toxic

Encephalomyelitis

Enteropathic spondylitis

Eosinophilic

granulomatosis with

polyangiitis

Erythema induratum

Erythema multiforme

Erythema nodosum

Evans syndrome

Expanded disability status scale score

decreased

Expanded disability status scale score

increased

Facial paralysis
Facial paresis
Felty's syndrome
Fulminant type 1
diabetes mellitus

Giant cell myocarditis

Glomerulonephritis membranoproliferative

Glomerulonephritis membranous

Glomerulonephritis rapidly progressive

Glossopharyngeal nerve

paralysis

Goodpasture's syndrome

Gout

Gouty arthritis
Gouty tophus

Granulomatosis with

polyangiitis

Guillain-Barre syndrome

Confidential

Medicago USA Page **50** of **55** 

endocrinopathy

enterocolitis

Immune-mediated

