**Uveitis** 

Vaccination site

vasculitis

Vagus nerve paralysis

Vascular purpura
Vasculitic rash
Vasculitic ulcer

Vasculitis

Vasculitis gastrointestinal

Vasculitis necrotising

VIth nerve paralysis

VIth nerve paresis

Vitiligo

Vocal cord paralysis

Vocal cord paresis

Vogt-Koyanagi-Harada

disease

Confidential

Medicago USA Page 53 of 55

Warm type haemolytic anaemia XIth nerve paralysis Radiculopathy

Medicago USA Page **54** of **55** 

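### The SAP counts potential immune-mediated diseases from a list that does not match the protocol's, and gives no rule for investigator-judged cases

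*SAP*

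**What the plan says.** The protocol sets the definition in Section 13.1.3.2.2:

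- The category is broad. Besides diseases of autoimmune origin it takes in "other inflammatory and/or neurologic disorders of interest which may or may not have an autoimmune aetiology".
- Section 19.5 supplies the list of diagnoses: "Adverse events that need to be recorded and reported as pIMDs include those listed in Section 19.5".
- The list can be extended at site level: "the Investigator will exercise their medical and scientific judgement in deciding whether other diseases have an autoimmune origin", and such a disease is then recorded as a pIMD too.
- Symptoms, signs or conditions that may or may not turn out to be a listed diagnosis are reported as ordinary adverse events, not as pIMDs, until the diagnosis is definite.
- Investigators are to receive a "list of preferred terms (PTs) and PT codes corresponding to the above diagnoses".

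The SAP sets the count. Section 9.3.4 splits AESIs into three separately tabulated categories: related hypersensitivity reactions found by standardised MedDRA queries, narcolepsy found by its preferred term, and "pIMDs and Other AESI (refer to Appendix 13.4". Appendix 13.4 is a long list in preferred-term style. It includes "Gouty arthritis" (beside gout and gouty tophus), anosmia and "Radiculopathy".

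The same SAP section provides a listing of all AESIs. The SAP does not mention the investigator-judgement route. The version history says that the pIMD list was updated and added as an appendix. Section 11, on changes in the planned analysis, does not mention it.

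**The concern.** The occurrence of AESIs is a primary safety endpoint in three periods (to Day 28, Day 29 to 182, Day 183 to 365). pIMDs are collected because the vaccine is adjuvanted, so this table is where a reader will look for an adjuvant signal. If its rows come from a list that is in places wider and in places narrower than the protocol's definition, the count in each group is not a count of what the protocol set out to measure. With about 40 subjects per group and few events expected, one subject can change how the comparison looks.

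**Working it through.** The plan states no figure here that could be reproduced, so the check is a side-by-side reading of protocol Section 19.5 and SAP Appendix 13.4, followed by a short calculation of what one subject is worth.

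**In the SAP list, not named in protocol Section 19.5**

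- Gout, gouty arthritis, gouty tophus. The musculoskeletal group in Section 19.5 covers lupus, scleroderma, inflammatory myopathies, rheumatoid and related arthritis, polymyalgia, spondyloarthropathies, polychondritis and mixed connective tissue disorder. None is a parent of gout, so these are not preferred-term expansions of a listed diagnosis.
- Anosmia. This is a symptom. The nearest heading is cranial nerve neuropathy.
- Radiculopathy. This is a non-specific nerve-root term. The nearest headings are myeloradiculoneuritis and the demyelinating neuropathies and plexopathies.
- Appendix 13.4 has other entries of the same kind: an antibody increase, changes in a disability score, and cardiomyopathy without the autoimmune qualifier that Section 19.5 attaches to it.

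**In protocol Section 19.5, not found in the SAP list**

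- Tolosa Hunt syndrome (neuroinflammatory disorders).
- Rosacea (skin disorders).

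The columns of Appendix 13.4 are disordered in the text examined, so these two absences should be confirmed in the original document. The additions do not depend on this, because they are legible.

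**Counting rule**

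- The protocol has two routes into the pIMD category: a Section 19.5 diagnosis, or investigator judgement of autoimmune origin.
- SAP Section 9.3.4 gives one reference, Appendix 13.4. The other two AESI categories in that section are term searches, so a programmer would naturally build the third as a match to the appendix.
- Built that way, a pIMD recorded on judgement under an unlisted term would reach the AESI listing but not the tables by group. An unlisted-in-protocol term such as gout would be counted if the event is in the database.

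**What one subject is worth**

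- In a planned group of 40: 1/40 = 2.5 percentage points.
- Across 120: 1/120 = 0.83 percentage points.

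**Illustration under an assumed rate.** The documents give no incidence for the added terms. If p is the assumed chance that a subject has at least one such event captured over the year, the chance of at least one such subject in a group of 40 is 1 − (1 − p)^40:

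- p = 0.5%: 18%
- p = 1%: 33%
- p = 2%: 55%
- p = 5%: 87%

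These figures show how strongly the answer depends on p. They are not an estimate for this trial.

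**The case against.** The strongest reply is that the protocol never closed its list. It says pIMDs include the Section 19.5 diagnoses, its general definition reaches inflammatory and neurologic disorders that need not be autoimmune, and it foresees a preferred-term list, which will be longer than a list of diagnoses. Anosmia and radiculopathy can be argued to sit near neurologic headings. Section 19 also calls the clinical documents in the appendices "meant as examples only; the actual documents used during the trial may differ slightly".

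Much of this stands, but it does not remove the mismatch. The preferred terms were to correspond to the listed diagnoses, and the only stated way to add a disease is investigator judgement, not a longer analysis list. The rule on symptoms and signs points against anosmia. The remark about examples fits the sample diary, memory aid and safety summary; Section 19.5 is used as a rule, since an event with enough evidence for one of its diagnoses must be reported as a pIMD. The words Other AESI in the table title do not help either, because the protocol's own heading ties that phrase to Section 19.5.

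A second reply is that the harm is limited. The tables are by system organ class and preferred term, so gout would show as its own row. Related events are also tabulated separately, safety analysis is descriptive without tests, and background events should fall on all randomised groups. After Day 28 an added term reaches the database only through a category still being collected, such as a medically attended event. All of this stands and keeps the point modest. It does not help a case that is missing from the table, and the headline count would still mix two definitions.

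A reader might go further and infer that the SAP drops investigator-judged cases. The documents do not support that. The SAP is silent and nowhere limits the table to Appendix 13.4. These cases are reported on the SAE/AESI form (protocol Section 13.1.6), so they are identifiable in the data.

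**Conclusion.** The point holds as a mismatch of definitions and a missing counting rule. Appendix 13.4 is wider than the protocol definition for the gout terms and for symptom-level or non-specific terms, and appears narrower for Tolosa Hunt syndrome and rosacea. Followed literally, Section 9.3.4 could over-count against the protocol definition and miss protocol-defined cases. Neither the difference nor its reason is given in SAP Section 11.

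The size is 2.5 percentage points for each subject wrongly in or out of a group of 40. The documents do not support a statement that the tables will fail to count what the protocol defines. That depends on how the table is programmed and on whether such events occur. Nor do they support an expected number of spurious events per group, since any such number rests on an assumed incidence.

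The conclusion assumes that the table is built by matching to Appendix 13.4. The claim about the two missing diagnoses also assumes that the original document confirms their absence.

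**What to change.** In SAP Section 9.3.4, count as a pIMD any event that the investigator reports as a pIMD on the SAE/AESI form, or that is coded to a preferred term mapping to a Section 19.5 diagnosis. Show the remaining Appendix 13.4 terms in a separate supportive row or table. Add to Appendix 13.4 any Section 19.5 diagnosis found to be missing once the original has been checked. Record the list difference and its reason in Section 11.

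The cost is one flag, one extra table and a late, documented SAP change. Some sponsor staff are unblinded during the study, so the change should be signed before the final database lock. Showing both counts avoids any appearance of having chosen a definition after seeing data.
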